Research hypothesis

Ho: The change in the score of the IIEF-EF scale in patients with moderate erectile dysfunction³, treated with radial wave therapy, is equal to those who receive placebo therapy.

Ha: The change in the score of the IIEF-EF scale increases at least five points in patients with moderate erectile dysfunction treated with radial wave therapy, compared with the score of patients receiving placebo therapy.

Study population

Patients diagnosed with erectile dysfunction of vascular origin who are treated at the Boston Medical Group facilities in Bogotá.

Inclusion criteria

- 1. Men older than 18 years
- 2. Erectile dysfunction presents for more than 3 months in more than 50% of intercourse.
- 3. IIEF-EF score between 11 and 21.
- 4. Patient who agrees to enter the study through the signing of an informed consent.

Exclusion criteria

- 1. EHS score of 4
- 2. Bladder, prostate or colon cancer.
- 3. Patients with ED of psychological origin.
- 4. Patients with spinal cord injury.
- 5. Patients with anticoagulant use.
- 6. Patients with sickle cell anemia.
- 7. Patients with clinical suspicion of hypogonadism (AMS greater than 36, Annex 1).
- 8. Patients with infections or active lesions of the penis or pubic area.
- 9. Patients with ED secondary to drug treatment (antiandrogenic therapy, antidepressants, use of corticosteroids, antiparkinsonians, antipsychotics).
- 10. Radical prostatectomy or other radical pelvic surgery.
- 11. Antecedents of pelvic radiotherapy.
- 12. Patients with penile implant.
- 13. Endocrine diseases that occur with ED: acromegaly, gigantism, Addison's disease, hyperprolactinemia, androgenic deficiency.
- 14. Patients with neurological diseases (Parkinson's, CVD, dementia of any origin)

³ For this study moderate erectile dysfunction is considered a score on the IIEF-EF scale from 11 to 21, which includes the mild to moderate and moderate categories.

Sample size

Assuming that the placebo plus drug group has an average change in the score of the IFE-EF scale of 5 points and that the new wave therapy must have an additional change of at least 5 points to be considered clinically relevant, for a power of 80% and a one-tailed level of significance of 97.5%, with a standard deviation of 8 points, a sample size of 33 patients was estimated for each group. Adjusting for a percentage of losses of 20%, the size per group is 40 patients, for a total of 80 patients in the study. These calculations were performed in Stata 15.1®.

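### With 20% losses, 40 men per group leaves 32, one fewer than the 33 the plan says it needs; the effect is about one point of power

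*Combined protocol and SAP*

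**What the plan says.** The whole calculation sits in the Sample size section. The design difference is 5 points on the IIEF-EF change ("the new wave therapy must have an additional change of at least 5 points to be considered clinically relevant"), "with a standard deviation of 8 points", "for a power of 80" per cent and "a one-tailed level of significance of 97.5" per cent. From these, "a sample size of 33 patients was estimated for each group". The loss step follows: "Adjusting for a percentage of losses of 20%, the size per group is 40 patients, for a total of 80 patients in the study".

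The section does not show how 33 became 40. Nothing elsewhere in the document replaces men who are lost, changes the 20%, or redefines the 33.

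**The concern.** A loss allowance is there so that, after the expected losses, the number left for analysis is at least the number the power calculation asked for. Here it is not. Taken as a share of the men enrolled, which is the ordinary meaning, a 20% loss leaves each arm below the plan's own target. The paragraph therefore states a loss rate that its sample size does not cover.

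The evaluable number matters because the Statistical Analysis section gives no method for missing outcomes. The email and telephone contact described under Follow-up is for the one-month visit. The primary IIEF-EF score is collected earlier, at the last treatment session, so that contact does not recover a missing primary value.

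**Working it through.** **Inputs, all from the Sample size section:** difference 5 points; SD 8 points; power 80%; a one-tailed level given as 97.5%, read here as one-sided alpha 0.025; 33 per group before losses; losses 20%; 40 per group enrolled.

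**Step 1: the plan's 40.** Multiplying up gives 33 × 1.20 = 39.6, rounded up to 40, which reproduces the stated figure.

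**Step 2: what 40 leaves.** 40 × (1 − 0.20) = 32, against a target of 33. The largest loss that 40 can absorb while keeping 33 is 1 − 33/40 = 17.5%.

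**Step 3: what the target needs.** 33/(1 − 0.20) = 41.25, rounded up to 42 per group, 84 in total. Check: 42 × 0.80 = 33.6, which covers 33. The gap to the plan is 2 enrolled men per group, 4 in total (4/80 = 5%).

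**Step 4: what one man per group costs in power.** The noncentrality is 5/(8 × √(2/n)). This is 2.539 for n = 33 and 2.500 for n = 32. The t figures use the noncentral t with 2n − 2 degrees of freedom. The normal figures are Φ(noncentrality − z), with z = 1.645 for one-sided 0.05 and z = 1.960 for one-sided 0.025.

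| One-sided alpha | Method | 33 per group | 32 per group | Loss in points |
|---|---|---|---|---|
| 0.05 | t | 80.7% | 79.6% | 1.1 |
| 0.05 | normal | 81.4% | 80.4% | 1.0 |
| 0.025 | t | 70.6% | 69.2% | 1.4 |
| 0.025 | normal | 71.9% | 70.5% | 1.4 |

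**Step 5: which level the 33 belongs to.** The number needed per group for 80% power is 33 (t) or 32 (normal) at one-sided 0.05, and 42 (t) or 41 (normal) at one-sided 0.025. Of the levels tried, only one-sided 0.05 (equivalently two-sided 0.10) with the t calculation returns exactly 33. The stated level does not. This is a separate and larger question about the base figure. It matters here only because it decides which power figure goes beside the 32.

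**The case against.** **It is too small to matter.** The effect is one evaluable man per group. Moving the assumed SD from 8 to 8.1 costs nearly as much: 33 per group then gives 79.8% (t, one-sided 0.05). The section gives no source for either the SD or the loss rate, and both are round planning figures. This stands as a judgement of size. It does not make 40 less 20% equal 33.

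**The mechanism is inferred.** A reader might conclude that the plan demonstrably multiplied by 1.2 where it should have divided by 0.8. The document does not show that, because it prints no formula. There is another route to 40: the normal approximation at one-sided 0.05 needs 32 per group, and 32/0.8 = 40. The stated 33 makes that route less likely but does not exclude it. The shortfall is the same whichever route was taken.

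**The promised power is not clearly missed.** A reader might also infer that 80% power fails even on the most favourable reading of the significance level. That is too strong. At one-sided 0.05, 32 per group gives 79.6% by t but 80.4% by the normal approximation. The t method is the better guide because it reproduces 33, yet even there the miss is 0.4 points.

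**The base figure is the bigger problem.** True. At one-sided 0.025, enrolling 42 per group to keep 33 would still give only about 71% power. Correcting the loss step alone does not repair the paragraph, and any fix must not present 33 as adequate at that level.

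**Conclusion.** The stated figures do not agree: 33 needed, 20% lost and 40 enrolled cannot all hold, since 40 leaves 32. The shortfall is one evaluable man per group, or 2 enrolled per group if 33 is to be kept, and costs 1.0 to 1.4 points of power depending on method and level. It rests on two assumptions: that the 20% is a share of men enrolled, and that lost men are neither replaced nor included in the primary analysis. The document contradicts neither.

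This is a minor but definite error in a stated sample-size figure, and it does not by itself make the trial underpowered. The gap between about 80% and about 69% power at 32 per group comes from the significance level, not from the loss step.

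**What to change.** Keep 80 patients and replace the loss sentence with wording such as: *40 patients per group will be enrolled (80 in total); with 20% losses, 32 per group are evaluable, which gives X% power for a 5-point difference with SD 8 at one-sided alpha Y.* With the t calculation, X is about 69 if Y is 0.025 and about 80 (79.6) if Y is 0.05. The level must be named, because the power figure means little without it.

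Two other edits are less good. Saying that 40 per group allows for losses of 17.5% fits the assumption to the number, and the document gives no reason to expect that rate. Raising enrolment to 42 per group restores the 33 but leaves open whether 33 is enough at the stated level.

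If the base figure is recalculated, divide by 0.8 for the loss step. For example, 42 evaluable per group would need 42/0.8 = 52.5, so 53 enrolled, whereas 42 × 1.2 = 50.4 would give 51 and repeat the shortfall.

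The cost of the main fix is one sentence and a less favourable stated power. No extra patients are needed.

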The research subjects will be followed up one month after the end of the treatment. In the event that the patient cannot attend the follow-up, the respective scales will be sent to his e-mail so he can process them and return them by the same means; if after 3 days no response is received, a research assistant will call him and apply the questionnaires by telephone.

Statistical Analysis

A descriptive analysis of the individuals' baseline characteristics linked to each treatment arm will be made, estimating measures of central tendency and dispersion in the case of continuous variables, and measures of relative and absolute frequency for categorical variables.

To evaluate the effectiveness of the therapy, the change in the IIEF-EF scale will be compared at the end of the treatment with the baseline score for each of the arms, using parametric tests in case the

data present a normal distribution, or nonparametric tests otherwise. This same analysis will be done for the scores at the one-month follow-up.

For the EHS scale, the change in at least 1 point will be evaluated, in any of the established measurements. The association between the change in the score and the received treatment will be evaluated estimating the relative risk with its respective confidence interval.

The percentage of patients that decrease or discontinue the use of sildenafil in each group will be estimated, comparing the proportion between the groups at the end of the therapy scheme and the month of follow-up, using the Chi-square test.

The incidence of adverse events for each of the intervention groups will be estimated and the value between them will be compared using the Chi-square test.

In addition to the comparison between groups, stratified analyzes will be performed with multivariate regression models to determine how each intervention adjusted for covariates, such as comorbidities or additional treatments.

An interim analysis will be done once 60% of the total number of patients has completed the treatment (main outcome).

Expected impact

The main contribution of this study is for the scientific community and for patients with erectile dysfunction, by collecting scientific evidence of quality that allows to make a decision about the use of radial waves for the management of erectile dysfunction.

Ethical aspects

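### The plan expects 20% losses but sets no analysis set or missing-data rule for IIEF-EF, so as written only men with a last-session score enter the primary result

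*Combined protocol and SAP*

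**What the plan says.** The Sample size section arrives at 33 evaluable men per group and then inflates: "Adjusting for a percentage of losses of 20%, the size per group is 40 patients". Its inputs are a control-arm change of 5 points, a further 5 points for radial waves, "with a standard deviation of 8 points", 80% power, and a "one-tailed level of significance of 97.5"%.

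The Statistical Analysis section describes the primary comparison in one sentence: "the change in the IIEF-EF scale will be compared at the end of the treatment with the baseline score for each of the arms", by a parametric or nonparametric test. For the later visit it adds: "This same analysis will be done for the scores at the one-month follow-up". I read this as a between-arm comparison of change, as the research hypothesis requires.

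The end-of-treatment IIEF-EF is completed at the last treatment session (Techniques, procedures, data collection and processing). Two provisions bear on missing data. Missing clinical information is to be taken from the electronic medical record at the end of collection. Men who miss the one-month visit are reached by e-mail and then by telephone (also under Follow-up). Nowhere does the document name an analysis set, an imputation rule, a model that uses incomplete records, or a missing-data sensitivity analysis.

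**The concern.** A change score cannot be computed without the later score. A test of change at one visit, with no rule for missing values, therefore analyses only men seen at that visit. With one man in five expected to be lost, that is a self-selected subset of the randomised groups.

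The comparison stays unbiased if loss is unrelated to response, or related to it in the same way in both arms. It does not if the arms differ. They could: the active arm's pressure varies with tolerance while the sham arm's is given as a single value with the wave blocked (Interventions), and the therapist knows the allocation (Randomization). If poor responders leave the active arm more often, the completer comparison favours radial waves; if they leave the sham arm more often, it works against them. Leaving the method open also means that it could be chosen after it is known who dropped out.

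**Working it through.** **1. The plan's sample size.** Inputs from the Sample size section: difference 5, SD 8, power 80%. With n = 2 × [8 × (z_alpha + z_power) / 5]² per group:

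- one-sided 0.05: 31.65, so 32 (33 with the t distribution);
- one-sided 0.025, which is how I read the stated 97.5% level: 40.19, so 41 (42 with the t distribution).

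The stated 33 matches one-sided 0.05, not the stated level.

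**2. The loss adjustment.** 33 × 1.2 = 39.6, rounded to 40, reproduces the plan. But 40 × 0.8 = 32. Keeping 33 after 20% losses needs 33 / 0.8 = 41.25, so 42 per group. Power by noncentral t for 5 points, SD 8:

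| Evaluable per group | One-sided 0.05 | One-sided 0.025 |
|---|---|---|
| 32 | 79.6% | 69.2% |
| 33 | 80.7% | 70.6% |

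**3. Completer bias in general.** Let d be the fraction lost in an arm and g the mean change in completers minus that in men lost. The completer mean exceeds the full-arm mean by d × g, so the bias in the arm difference is d1 × g1 − d0 × g0 (1 = active, 0 = sham). The 20% is from the plan, applied here to the last-session score; the g values and the unequal loss rates are assumptions.

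| Loss, active / sham | g1 | g0 | Bias (points) |
|---|---|---|---|
| 20% / 20% | 5 | 5 | 0.2 × 5 − 0.2 × 5 = 0 |
| 20% / 20% | 2.5 | 0 | 0.5 |
| 20% / 20% | 5 | 0 | 1.0 |
| 20% / 20% | 10 | 0 | 2.0 |
| 30% / 10% | 5 | 5 | 1.5 − 0.5 = 1.0 |

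Exchanging the arms reverses the sign.

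**4. Simulated mechanisms, and what a two-visit model recovers.** Assumptions: SD 8, correlation 0.7 between the two post-baseline scores, 20% missing the last-session score, missingness related to response in the active arm only (logit slope per SD as shown) and random in sham.

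| Loss depends on | Slope | Completer bias | Two-visit model, all of these men answer at one month | Two-visit model, half answer |
|---|---|---|---|---|
| One-month score | 1 | 0.98 | 0.01 | 0.44 |
| Last-session score itself | 1 | 1.39 | 0.75 | 1.04 |
| Last-session score itself | 0.5 | 0.77 | 0.41 | 0.57 |

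With loss depending on the one-month score at slope 0.5, the completer bias is 0.54.

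Share of bias removed: in the first row (0.98 − 0.01) / 0.98 = 99%, or (0.98 − 0.44) / 0.98 = 55%; in the second (1.39 − 0.75) / 1.39 = 46%, or (1.39 − 1.04) / 1.39 = 25%. The first row is favourable by construction: given the one-month score that the model uses, the data are missing at random.

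**5. Consequence for error.** With 32 per arm, SD 8 and no true effect, the false-positive rate in favour of radial waves would be:

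| Bias (points) | Nominal one-sided 0.025 | Nominal one-sided 0.05 |
|---|---|---|
| 0.5 | 4.3% | 8.1% |
| 1 | 7.1% | 12.5% |
| 2 | 16.5% | 25.6% |

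These rates are conditional on the assumed bias.

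**The case against.** The strongest reply is that no particular bias follows from the documents. Informative loss in one arm only, the slope and the correlation are all assumptions, and equal mechanisms give zero. Patients, physicians and questionnaire staff are blind, which limits differential exit. Adjusting pressure to tolerance could keep men in the active arm rather than drive them out, and leaving for poor tolerance is not leaving for poor response. Sham non-responders may leave too, offsetting or reversing the bias. All of this stands. A reader might infer that the primary result will be about 1 point too favourable to radial waves; the documents support neither that size nor that direction.

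A reader might also infer that the plan prescribes a completers-only analysis. It does not say so; that is what the written method yields when nothing else is specified.

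The existing retrieval steps are real but do not close the gap. A medical record cannot supply a questionnaire that was never completed, the e-mail and telephone route is given only for the one-month visit, and neither step is an analysis rule.

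It can fairly be said that a repeated-measures model is not the only acceptable choice; baseline-adjusted analysis with multiple imputation would also serve. Nor is the model a complete cure, as step 4 shows.

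Lastly, 32 rather than 33 costs about one percentage point of power. Treating it as a material shortfall would be wrong, particularly as 33 does not meet the plan's own significance level.

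**Conclusion.** The concern holds as an omission with a real but unquantified risk. The plan expects 20% losses, and its only IIEF-EF analysis uses one visit at a time with no analysis set or missing-data rule. The resulting bias is about 0 if loss works the same way in both arms, about 0.5 to 1.4 points in the simulated one-arm scenarios, and up to about 2 points if completers and lost men differ by 10 points in one arm only. These are conditional figures, not predictions. Using both post-baseline scores removes between about a quarter and nearly all of the bias, depending on the mechanism and on how many men without a last-session score answer at one month. The change should be made, because the method must be fixed before the losses are seen. The 32-versus-33 arithmetic is a side note.

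**What to change.** In Statistical Analysis, state that the primary analysis concerns all randomised men in the arm assigned. Specify one likelihood-based repeated-measures model of the end-of-treatment and one-month IIEF-EF scores, with arm by visit and baseline IIEF-EF; the primary estimate is the arm difference at end of treatment.

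Add one sensitivity analysis that progressively lowers the unobserved active-arm end-of-treatment scores, because the model does not correct loss that depends on the unseen score. It should include men with neither post-baseline score, who add nothing to the baseline-adjusted model. With 20% missing in that arm, each 5-point reduction lowers the estimated difference by 0.2 × 5 = 1 point, so the report can show how far the scores must fall before the conclusion changes.

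In Sample size, restate that 40 per group with 20% losses leaves 32 evaluable, and give the power with it: 79.6% at one-sided 0.05 and 69.2% at the stated one-sided 0.025.

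The cost is SAP wording, a slightly longer model and a less favourable stated figure. No new patients or visits are needed. Extending the e-mail and telephone collection to the last-session questionnaire would reduce the missing data at source, at the price of a small procedural change.

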Interventions

Each patient will be assigned randomly to one of the following groups:

- Arm 1 (Radial wave therapy + oral treatment): 6 radial waves' sessions. A weekly session of radial waves will be applied with the following parameters: 6000 pulses at 1.5-2.6 bar (depending on patient tolerance), with a frequency of 17Hz, the frequency should increase to 22HZ the first 500 impulses to create mild anesthesia in the area; in all the sessions of radial waves, 4000 impulses will be distributed in the body of the penis in scanning technique and 2000 impulses in the perineal area, specifically in the ischiocavernosus and bilateral bulbo-sponge muscles. During the period of therapy application, patients will receive oral treatment with sildenafil 4 according to the patient's degree of affectation.
- Arm 2 (Placebo therapy + oral treatment): 6 sessions of placebo therapy. There will be a weekly session of placebo wave therapy, using the respective device to prevent the patient from receiving the radial wave. The same parameters of the "real" therapy will be used: 6000 pulses at 2.6 bar, with a frequency of 17 Hz; in all the sessions of radial waves, 4000 impulses will be distributed in the body of the penis in scanning technique and 2000 impulses in the perineal area. During the period of therapy application, patients will receive oral treatment with sildenafil 5 according to the patient's degree of affectation.

The radial waves will be administered with the Masterpuls MP50 device from Storz medical.

Primary Outcome

The primary outcome of this study is the difference in the average score of the IIEF-EF scale (Annex 3) in at least 5 points at the end of the treatment.

Secondary outcomes

- IIEF-EF score after one month of follow-up.
- Erection Hardness Score (EHS) at the end of treatment and one month follow-up: The EHS is a unique Likert scale and the version validated in Spanish (35) will be used, which has the following score, 0: The penis does not change in size or hardness; 1: The penis increases in size but does

⁴ This is the standard treatment.

⁵ This is the standard treatment

not become rigid; 2: The penis is rigid but not enough to penetrate; 3: The penis is rigid enough for penetration but not completely hard; and 4: The penis is completely hard or rigid (Annex 4).

- Change in the dose or use of sildenafil.
- Incidence of adverse events.

Safety

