It will be determined by the presence of adverse events. These will be evaluated at the end of each of the therapies and a month of follow-up. This variable will be dichotomous as the presence or absence of adverse events. Additionally the type of adverse event and the degree of severity will be recorded.

Randomization

The assignment of patients to the treatment arms will be done with the method of randomization by balanced blocks of unequal cells. The assignment of the treatment will be centralized, so once the patient agrees to participate in the study and signs the informed consent, an email should be sent to the research center ([contact]) who will only inform the therapist which is the group (intervention or control) that corresponds to the patient.

To conceal the assignment sealed opaque envelopes will be used, this envelope will be opened once the request is generated in each center, after the patient has voluntarily accepted to participate in the study and the informed consent process has been carried out with signature of the written document.

Neither the patient, the attending physician, nor the professional who applies the questionnaires will know the group to which the patient was assigned.

Techniques, procedures, data collection and processing

The subjects who attend consultation for erectile dysfunction at the Boston Medical Group clinics in Bogotá (Colombia) and Lima (Peru), will be treated as usual according to the institutional management protocols and screened to determine if they meet the eligibility criteria. If so, they will be invited to participate in the research project and the informed consent process will be carried out in which the objectives, risks, benefits, procedures and other relevant research data will be explained.

Once the patient has voluntarily accepted to participate in the study and the informed consent document has been signed, an email will be generated to the research center to request the group to which the patient will be assigned.

A baseline measurement of the IIEF-EF and the EHS will be made before starting the intervention; In addition, the AMS questionnaire should be completed to rule out hypogonadism. Once the treatment is completed, patients must complete the IIEF-EF and EHS scales in the last treatment session. In this same session, the patient will be evaluated for adverse events; later, they will have

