a medical follow-up one month after the end of the treatment, in which measurements of effectiveness and safety of the therapy will be made again. If the patient cannot attend the medical follow-up, the surveys will be sent by email on the day of the follow-up appointment and the patient will be contacted by telephone (Figure 2).

Radial wave therapy will be applied with the following parameters: There will be a weekly session of 6 sessions of radial waves. A weekly session of radial waves will be applied with the following parameters: 6000 pulses at 1.5-2.6 bar (depending on patient tolerance), with a frequency of 17Hz, the frequency should increase to 22HZ the first 500 impulses to create mild anesthesia in the area; in all the sessions of radial waves, 4000 impulses will be distributed in the body of the penis in scanning technique and 2000 impulses in the perineal area. The application at the perineal level should be performed with the patient in the supine position in a low lithotomy position, the testicles should be slightly raised to apply the wave on the perineal musculature (ischiocavernosus and bilateral bulbospongiosus).

The placebo therapy will be done with the same machine and the same parameters as the actual therapy, but the adjustment will be made in the handpiece to eliminate the effect of the radial waves.

If there is a difference between placebo therapy and radial wave therapy, patients in the placebo arm will receive the intervention arm scheme, one month after the initial treatment.

All clinical data will be recorded in the electronic medical record of Boston Medical Group and in the database of the study, in the latter a code will be used for the identification of research subjects, thus avoiding the use of the personal patient data. At the end of the collection of the total sample, the missing clinical information will be extracted from the electronic medical record. This information will be exported to a flat file for the corresponding statistical analysis.

The research team will hold meetings every two weeks to monitor the study to validate the data of the base.

Follow-up

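### The sham is said to use the active settings, but the settings listed for it differ in pressure and pulse rate, leaving a possible cue to allocation

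*Combined protocol and SAP*

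**What the plan says.** The combined protocol and SAP describes the active sessions in three places: the Abstract, Interventions (Arm 1), and Techniques, procedures, data collection and processing. All three give "6000 pulses at 1.5-2.6 bar (depending on patient tolerance), with a frequency of 17Hz" and add that "the frequency should increase to 22HZ the first 500 impulses to create mild anesthesia in the area".

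The sham settings are listed in two places, the Abstract and Interventions (Arm 2). Both first state that the settings are those of the real therapy. Both then give "6000 pulses at 2.6 bar, with a frequency of 17 Hz", with no tolerance range and no 22 Hz phase.

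The procedures section makes a general statement instead: "The placebo therapy will be done with the same machine and the same parameters as the actual therapy". The one difference it names is that "the adjustment will be made in the handpiece to eliminate the effect of the radial waves".

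The schedule is the same in both arms, 6 sessions at weekly intervals; for Arm 2, "There will be a weekly session of placebo wave therapy".

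On blinding, the Randomization section says: "Neither the patient, the attending physician, nor the professional who applies the questionnaires will know the group". The therapist is told the allocation. The primary outcome is the IIEF-EF at the end of treatment, and patients complete it at their final session.

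**The concern.** The sham is the only means by which this trial can keep patients unaware of whether they receive radial waves, since both arms also take sildenafil. A sham serves that purpose best when the session runs the same way in both arms apart from the blocked wave. The protocol states that intention and then lists settings that depart from it in two respects.

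A therapist working from the Arm 2 list would run fixed pressure and one constant pulse rate. A therapist working from the procedures section would run whatever the active arm runs. Clinics in Bogotá and Lima are named in the procedures section, so different therapists could deliver different shams, each with support in the text.

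The IIEF-EF and the EHS are both the patient's own report. If the sessions run differently by arm, a patient who knows what the active routine involves has a possible clue to his allocation. An unblinded therapist who sets pressure by tolerance in one arm only may also handle the two groups differently. Either could let expectation into the primary comparison.

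**Working it through.** No figure in the plan depends on this point, so the check is a comparison of the texts, with simple arithmetic to describe the difference in the sessions.

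**Side by side**

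| Feature | Active (Abstract; Interventions, Arm 1; procedures) | Sham list (Abstract; Interventions, Arm 2) | Sham, general statement (procedures) |
|---|---|---|---|
| Impulses | 6000 | 6000 | same as active |
| Pressure | 1.5 to 2.6 bar, by tolerance | 2.6 bar, fixed | same as active |
| Pulse rate, first 500 | 22 Hz | 17 Hz | same as active |
| Pulse rate, remaining 5500 | 17 Hz | 17 Hz | same as active |
| Handpiece | normal | device used to block the wave | adjusted to remove the effect |

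The second and third columns agree on impulse count and on the main pulse rate. They disagree on pressure and on the opening pulse rate. The fourth column agrees with the second on every setting, and therefore conflicts with the third on those two rows. The sham list also conflicts with its own opening words, which announce sameness.

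**Size of the difference if the Arm 2 list is followed**

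Inputs: impulse counts, pulse rates and pressures from Interventions. Assumptions: impulses are delivered without pauses, and 22 Hz applies to all of the first 500.

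- Pressure: the active setting may be as much as 2.6 − 1.5 = 1.1 bar below the sham setting, or it may equal it, depending on the patient.
- Pulse rate in the opening phase: 22/17 = 1.29, so 29% faster in the active arm.
- Share of the session affected by the rate difference: 500/6000 = 8.3% of impulses.
- Duration of the first 500 impulses: 500/22 = 22.7 s active; 500/17 = 29.4 s sham.
- Total duration: 500/22 + 5500/17 = 346.3 s active; 6000/17 = 352.9 s sham. The gap is 6.7 s, about 2%.
- Recurrence: the settings apply to each of the 6 sessions.

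Session length is therefore not a useful cue. What differs is the drop in pulse rate after the first 500 impulses, and whether pressure depends on the patient's tolerance.

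**What the documents do not give**

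They describe no mock tolerance setting or mock rate change for the sham and no check of blinding. They give no size for any effect of expectation on the IIEF-EF.

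**The case against.** The strongest reply is that this is a drafting shortcut. The procedures section gives the full active routine, including the tolerance range and the 22 Hz start, and shortly afterwards says the sham uses the same parameters. On that text the pulse-rate sequence is already matched. The Arm 2 list may be an abbreviation: in Interventions it also omits the perineal muscles that Arm 1 names. This is plausible, and the procedures section may well express the intention. But the Arm 2 list is the explicit specification for that arm, it appears twice with the same two departures, and it states a single pressure where the active arm has a range. The text does not settle which statement governs.

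A second reply is that each patient sees only one arm. This stands. A reader might infer that patients will be able to tell their arm at every session. The documents do not support that: a rate change, or its absence, is informative only to someone who knows what the active session involves. Procedures are explained at consent, but the level of detail is not given. The supportable statement is that a possible cue exists.

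A reader might also infer that active-arm therapists question patients about tolerance and alter the setting during the session. The protocol says only that pressure depends on tolerance. It describes no question, no adjustment within a session and no script for either arm.

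Finally, a reader might want to express the problem as an inflated false-positive rate. Any such figure would rest on an assumed shift in IIEF-EF that nothing in the documents links to these settings, so none is given here.

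**Conclusion.** Wrong as written: an internal contradiction that bears on blinding. The sham list departs from the active settings in pressure and in the opening pulse rate, while the protocol says the parameters are the same and that only the handpiece is adjusted.

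If the Arm 2 list is followed, sessions differ between arms by up to 1.1 bar and by a 29% faster rate for about 23 s, in each of 6 sessions. That makes a cue to allocation, or unequal handling by the unblinded therapist, possible. It does not show that blinding fails, and the effect on the primary comparison cannot be sized from the documents. If therapists instead follow the procedures section, the settings match and the defect is one of wording only.

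The point deserves correction because the therapist is unblinded, the primary outcome is the patient's own report, and the remedy costs almost nothing.

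**What to change.** Reconcile the Abstract, Interventions (Arms 1 and 2) and the procedures section so that the sham description agrees with the protocol's own statement that the parameters are the same and only the handpiece differs. Which pressure and pulse-rate settings apply is for the sponsor to confirm; this review does not choose them.

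Once they are confirmed, have therapists follow one written session script in both arms, so that the steps a patient sees and hears do not depend on allocation.

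The cost is protocol wording and a shared script. No equipment is added, because both arms already use the same machine. One limit remains: the documents do not say how the adjusted handpiece feels to the patient, so agreement on settings removes an avoidable difference but does not by itself establish that the sham is convincing.
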